#### **1.3.2.1 Co-Primary Efficacy Analysis**

The co-primary measures of efficacy will be:

- The proportion of subjects who are in endoscopic remission (Endoscopic Score  $\leq 1$ ), and
- The proportion of subjects who achieve a Stool Frequency Score  $\leq 1$ , at Week 10.

The proportion of subjects who achieve each of the co-primary measures of efficacy at Week 10 will be presented and compared between treatment groups using a Cochran-Mantel-Haenszel test accounting for region. The difference in proportions between the two groups and associated 95% confidence interval will also be presented.

Subjects with a missing endoscopic assessment at week 10, or insufficient stool frequency data, will be declared not to have achieved the respective outcomes.

Secondary analyses of the co-primary endpoints will include investigations of the effect of treatment and baseline characteristics (region, treatment, sex, age group, PDAI score) on the co-primary endpoints using logistic regression models.

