#### **1.3.2.2 Secondary and Tertiary Efficacy Analyses**

##### **Stool Frequency**

The mean daily stool frequency (frequency of bowel movement) will be evaluated from the data recorded in the subject's diary using the data from the 7 days prior to each study visit. Mean frequency and change from baseline will be summarized.

The change from baseline at each study visit will be analyzed using a mixed effects repeated measures analysis of covariance (ANCOVA) model of the change from baseline with region, treatment, Visit, treatment\*Visit interaction, sex and age group as fixed effects and baseline value as covariate.

The proportion of subjects with a Stool Frequency Score equal to 0 ('Normal number of stools per day for the subject') will be summarized and analyzed in the same way as for the co-primary endpoints.

The time to clinical remission will be summarized using Kaplan-Meier methods. Subjects without remission, (including those who withdrew from the study without remission) will be censored at the time of last assessment of the Stool Frequency Score. Kaplan-Meier curves

will be presented with estimates of the probability of remaining remission-free at Weeks 3, 6 and 10 together with their 95% confidence intervals. The time to clinical remission will be investigated using a Cox proportional hazards regression model including terms for region, treatment, sex, age group, and the baseline mean number of bowel movements per day.

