### **PDAI**

The PDAI will be assessed at Day 1 and Weeks 6 and 10. The separate domain scores and the overall score, together with their change from baseline, will be calculated at each visit and summarized by treatment group.

The change from baseline for each PDAI domain score and for the overall score, will be analysed using the same repeated measures ANCOVA model as for the mean number of bowel movements per day.

Estimates of the following proportions of subjects will be evaluated at Weeks 6 and Weeks 10:

- Those who achieve an overall PDAI score  $<5$
- Those who achieve an overall PDAI score  $<3$
- Histological Improvement, defined as a PDAI Histology Score  $\leq 1$  (for subjects with a baseline score  $>1$ ), or with at least a 2-point improvement from baseline
- Histological Healing, defined as a PDAI Histology Score of 0 for subjects that had a baseline subscore above 0.

Each of these proportions will be compared between treatment groups at each visit using a Cochran-Mantel-Haenszel test accounting for region. In addition, they will be analyzed using separate logistic regression models for Week 6 and Week 10. These models will include terms for region, treatment, sex, age group and the corresponding baseline PDAI score.

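### The secondary logistic models for the two co-primary endpoints omit each outcome's own baseline and do not say which PDAI score they use

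*SAP*

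**What the plan says.** Section 1.3.2.1 defines two different co-primary outcomes at Week 10: "The proportion of subjects who are in endoscopic remission" (Endoscopic Score of 1 or less) and "The proportion of subjects who achieve a Stool Frequency Score" of 1 or less. Each is "compared between treatment groups using a Cochran-Mantel-Haenszel test accounting for region", with no other baseline covariate.

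The same section then adds supportive models: "Secondary analyses of the co-primary endpoints will include investigations of the effect of treatment and baseline characteristics", with the covariates listed as "region, treatment, sex, age group, PDAI score) on the co-primary endpoints using logistic regression models". One list serves both outcomes, and PDAI is its only disease-severity term.

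The models in section 1.3.2.2 are built differently:

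- **Stool Frequency:** the repeated-measures ANCOVA has the baseline value as covariate. The Cox model for time to clinical remission includes sex, age group, "and the baseline mean number of bowel movements per day".
- **Urgency:** the logistic models include baseline urgency.
- **PDAI responder proportions:** "These models will include terms for region, treatment, sex, age group and the corresponding baseline PDAI score".
- **Quality of life:** the same ANCOVA as for stool frequency, hence the own baseline value.
- **Pouchitis intervention:** the Cox model uses baseline PDAI, for an outcome that has no baseline value of its own.

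**The concern.** A baseline measurement of the outcome is often among its better predictors. The SAP acts on this for most secondary outcomes but not for the two on which the superiority claim rests. The contrast is sharpest for stool frequency: baseline bowel movements enter the time-to-remission model but not the Week 10 responder model. The analysis of a Stool Frequency Score of 0, which is to follow the co-primary analysis, inherits the gap.

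The PDAI term is also undefined. The PDAI section separates overall, domain and histology scores; section 1.3.2.1 does not. The overall score is the natural reading, but it is an inference. If a domain score is meant, the SAP does not say which. Under either reading, diary-based stool frequency is not named.

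At stake are some precision in the adjusted treatment comparison, and a covariate choice left open until late in the trial.

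**Working it through.** **1. The plan's own figures.** Section 1.2 assumes 50% versus 20%, two-sided 5%, 95% power per endpoint. With mean proportion 0.35:

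n = [1.960·√(2·0.35·0.65) + 1.645·√(0.5·0.5 + 0.2·0.8)]² / 0.30² = [1.322 + 1.053]² / 0.09 ≈ 62.7, so 63 per group, as stated.

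The continuity-corrected formula gives 70 against the stated 69, a trivial difference. The joint figure is 0.95² = 0.9025, stated as 90%. Power at 69 per group without continuity correction is 0.966 per endpoint. None of these figures uses the covariate list of the logistic models.

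**2. Are the baselines available?** Stool frequency is recorded in the diary, and the Cox model already uses its baseline. The PDAI is assessed at Day 1, and "The separate domain scores and the overall score, together with their change from baseline, will be calculated at each visit". A baseline endoscopic score is therefore likely to exist. However, the SAP neither lists the PDAI domains nor says that the co-primary Endoscopic Score is one of them.

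**3. One covariate at a time.** Simulated logistic models, 69 per group, 3,000 trials per scenario. Assumptions, none given in the SAP: log-odds slope of the own baseline 0 to 1.2 per SD; correlation of PDAI with the own baseline 0.5 or 0.8; no prognostic value in the rest of PDAI. The standardised risk difference is the mean predicted probability with all subjects set to alicaforsen, minus the mean with all set to placebo. Power:

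| Own-baseline slope | 50% v 20%: PDAI | 50% v 20%: own baseline | 40% v 20%: PDAI | 40% v 20%: own baseline |
|---|---|---|---|---|
| 0 | 0.967–0.968 | 0.966–0.967 | 0.737–0.739 | 0.732–0.736 |
| 0.4 | 0.962–0.966 | 0.966–0.968 | 0.730–0.745 | 0.743–0.749 |
| 0.8 | 0.968–0.973 | 0.977–0.978 | 0.749–0.762 | 0.773–0.778 |
| 1.2 | 0.971–0.978 | 0.983–0.986 | 0.743–0.792 | 0.812–0.823 |

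At the planned effect the difference is about 0 to 1 point. At 40% versus 20% it reaches 3 to 7 points, but only with a strongly prognostic baseline.

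**4. Where the gain appears.** At 50% versus 20%, slope 1.2 and correlation 0.5, the SE of the log odds ratio rises from 0.410 (PDAI) to 0.467 (own baseline). The SD of the standardised risk difference falls from 0.0755 to 0.0708, a variance ratio of (0.0708/0.0755)² = 0.88. The gain shows in power and in the risk difference, not in the SE of the log odds ratio.

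**5. Replace PDAI, or add to it?** Step 3 gives the rest of PDAI no prognostic value. If it has some (latent correlation 0.3 with the outcome), the order can reverse. At 42% versus 20% with own-baseline correlation 0.3, PDAI cuts the variance by about 10% and the own baseline by about 4%. Power is 0.84 to 0.85 against 0.83. Replacement can therefore lose precision.

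For adding the own baseline beside PDAI, the assumed latent correlations were 0.3 to 0.5 for the own baseline with the outcome, 0.4 to 0.7 between the own baseline and PDAI, and 0 to 0.3 for the rest of PDAI with the outcome. Compared with PDAI alone:

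- further variance reduction: about 0 to 13 percentage points, and never materially worse;
- power: about 0 to 1.5 points more at 50% versus 20%, and about 0 to 5 at 42% versus 20%.

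**6. Cost of an uninformative term.** In step 3 with slope 0, at 50% versus 20% and correlation 0.5, the SD of the risk difference goes from 0.0756 with no covariate to 0.0760 with one: 0.0760/0.0756 = 1.005, or about 0.5%.

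**The case against.** The strongest reply is that no decision depends on these models. Success requires both CMH tests to be significant. The logistic models are secondary and partly meant to explore predictors, and their covariate list is worded as open. Section 1.4 also provides for a blinded review of additional covariates before the SAP is finalised. All of this stands and keeps the point minor. It does not remove it: the section 1.4 review is generic, names no covariate and does not settle which PDAI score is meant.

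A second reply is that a Stool Frequency Score of 0 means a normal number of stools for that subject, so raw bowel movements per day is not strictly the outcome's own baseline. That is correct. The baseline Stool Frequency Score is the closer match, while bowel movements per day is the related measure the SAP already uses. Either will serve if it is named in advance.

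Three stronger readings are tempting and not supported:

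- **That overall PDAI is a diluted proxy and should be replaced.** The SAP has no prognostic data to show this, and step 5 reverses it under plausible assumptions.
- **That the trial loses power for its primary claim.** The CMH test does not use these covariates.
- **That adjustment would tighten the odds ratio.** Its standard error on the log scale rises.

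**Conclusion.** The point holds as a low-cost improvement to secondary analyses. One unlabelled PDAI term serves two different outcomes, and neither outcome's own baseline is included, contrary to the SAP's usual pattern.

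The benefit of adding that baseline runs from nothing to modest. It is largest when the baseline is strongly prognostic, the rest of PDAI is not, and the true effect is smaller than planned. At the planned effect, unadjusted power per endpoint is already about 0.97, which leaves little to gain. The ranges in step 5 rest wholly on assumed correlations. The document supports the inconsistency and the ambiguity, but no particular size of loss.

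**What to change.** In section 1.3.2.1, before unblinding:

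1. Keep the PDAI term and state that it is the baseline overall score.
2. Add to the stool-frequency model either baseline mean bowel movements per day or the baseline Stool Frequency Score, naming one. Apply the same model to the analysis of a Stool Frequency Score of 0.
3. Add the baseline endoscopic score to the endoscopic-remission model, after confirming that it is recorded at baseline with the PDAI.
4. Report the model-standardised risk difference with its 95% CI as a secondary result beside the CMH test.

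The cost is SAP wording and one more term per model, with negligible loss if that baseline proves uninformative. No extra subjects are needed, and no new data if step 3 is confirmed. The primary test and the sample size stay as they are.

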#### **1.3.2.2 Secondary and Tertiary Efficacy Analyses**

##### **Stool Frequency**

The mean daily stool frequency (frequency of bowel movement) will be evaluated from the data recorded in the subject's diary using the data from the 7 days prior to each study visit. Mean frequency and change from baseline will be summarized.

The change from baseline at each study visit will be analyzed using a mixed effects repeated measures analysis of covariance (ANCOVA) model of the change from baseline with region, treatment, Visit, treatment\*Visit interaction, sex and age group as fixed effects and baseline value as covariate.

The proportion of subjects with a Stool Frequency Score equal to 0 ('Normal number of stools per day for the subject') will be summarized and analyzed in the same way as for the co-primary endpoints.

The time to clinical remission will be summarized using Kaplan-Meier methods. Subjects without remission, (including those who withdrew from the study without remission) will be censored at the time of last assessment of the Stool Frequency Score. Kaplan-Meier curves

will be presented with estimates of the probability of remaining remission-free at Weeks 3, 6 and 10 together with their 95% confidence intervals. The time to clinical remission will be investigated using a Cox proportional hazards regression model including terms for region, treatment, sex, age group, and the baseline mean number of bowel movements per day.

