### **1.1.2 Hypothesis Testing and Confidence Intervals**

All significance probabilities will be two tailed. Statistical tests will be at a 5% level of significance.

Confidence intervals will be 95% two-sided.

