### **Quality of Life Questionnaire**

Quality of life is assessed using the CGQL (at baseline and Weeks 6, 10, 18 and 26) and EQ-5D-5L (at baseline, Week 6 and Week 10).

The change from baseline for each CGQL and EQ-5D domain score, and for the overall scores, will be summarized by study visit.

The Total CGQL Score and the EQ-5D Index score will be analysed using the same repeated measures ANCOVA model as for the mean number of bowel movements per day.

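### The repeated measures ANCOVA gives baseline one slope for all visits; if the slope differs between visits, the secondary treatment contrasts lose a little precision that a baseline-by-visit term would recover

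*SAP*

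**What the plan says.** The model is defined once, in section 1.3.2.2 under Stool Frequency: "The change from baseline at each study visit will be analyzed using a mixed effects repeated measures analysis of covariance (ANCOVA) model". Its terms are region, treatment, visit, treatment-by-visit, "sex and age group as fixed effects and baseline value as covariate". No baseline-by-visit term is listed.

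Two other subsections of 1.3.2.2 take the model over by reference:

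- **PDAI** domain and overall scores, assessed after baseline at Weeks 6 and 10, use it: "will be analysed using the same repeated measures ANCOVA model as for the mean number of bowel movements per day".
- **Quality of Life Questionnaire:** "The Total CGQL Score and the EQ-5D Index score will be analysed using the same repeated measures ANCOVA model". CGQL is collected after baseline at Weeks 6, 10, 18 and 26, and EQ-5D at Weeks 6 and 10.

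For stool frequency the visits are not listed with the model. The same subsection asks for "estimates of the probability of remaining remission-free at Weeks 3, 6 and 10", so Weeks 3, 6 and 10 are taken here as the minimum set.

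The SAP states no within-subject covariance structure, no SDs and no correlations between baseline and later visits. The co-primary endpoints do not use this model. Under section 1.3.2.1 they are "compared between treatment groups using a Cochran-Mantel-Haenszel test accounting for region".

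**The concern.** The model lets the treatment effect change from visit to visit but holds the baseline effect constant. If baseline predicts an early value better than a late one, a single slope is a compromise that adjusts too much at some visits and too little at others. Part of the chance imbalance in baseline between the arms is then left in, or over-corrected, at each visit, and the contrast is noisier than it need be.

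A falling slope is plausible for a diary count in a trial that expects some subjects to return to normal and others not, but the SAP contains no figure that shows it. What is at stake is a modest amount of precision in secondary contrasts, from data the trial collects anyway.

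**Working it through.** **The plan's own figures.** None is given for this model. The only sample size is for the co-primaries (50% vs 20%, two-sided 5%, 95% power). The usual two-proportion formula gives 63 per group without and 70 with continuity correction, against 63 and 69 stated, and 0.95 × 0.95 = 0.9025. These have no bearing on the point beyond supplying the total of 138.

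**Formula.** Let β_k be the true baseline slope at visit k, σ_k² the residual variance there, and b the single slope the model estimates. The residual at visit k then carries an extra (β_k − b) × baseline. Randomisation makes baseline independent of arm, so no bias arises, but the variance of the contrast is multiplied by

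VR_k = 1 + (β_k − b)² · var(baseline) / σ_k².

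With unit SDs, β_k is the correlation ρ_k and σ_k² = 1 − ρ_k². Analysing change instead of the raw value lowers every slope by 1 and leaves VR_k as it is.

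Under compound symmetry b is the simple mean of the β_k. Under an unstructured covariance it is the limiting GLS slope, b = 1′W⁻¹β / 1′W⁻¹1, with W the residual covariance plus (β − b)(β − b)′, solved by iteration. Residual correlations between visits of 0.3, 0.5 and 0.7 were tried.

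**Assumed inputs (none is in the SAP).** Correlations with baseline as shown, complete data, and sex, age group and region ignored.

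**Stool frequency, Weeks 3/6/10, correlations 0.7/0.55/0.4, Week 10:**

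| Setting | b | Week 10 variance ratio |
|---|---|---|
| Equal SDs, unstructured | 0.591 / 0.6115 / 0.6565 | 1 + (b − 0.4)²/0.84 = 1.043 / 1.053 / 1.078 |
| SDs 1/1.15/1.3, unstructured | 0.663 / 0.683 / 0.719 | 1 + (b − 0.52)²/1.42 = 1.014 / 1.019 / 1.028 |
| Equal SDs, compound symmetry | 0.55 | 1 + 0.15²/0.84 = 1.027 |
| Equal slopes | common value | 1.000 |

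In the second row β at Week 10 is 0.4 × 1.3 = 0.52 and σ² is 1.3² × 0.84 = 1.42. In the first row the loss equals 138 × (1 − 1/1.043) ≈ 6 to 138 × (1 − 1/1.078) ≈ 10 subjects.

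**Which visit loses most.** Under compound symmetry with the same inputs, Week 3 gives 1 + 0.15²/0.51 = 1.044, more than the 1.027 at Week 10. Under the unstructured covariance with equal SDs the order is reversed.

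**Other rates of fall (equal SDs, Week 10).** 0.6/0.5/0.4 gives 1.016 to 1.023 unstructured. A steep 0.8/0.5/0.2 gives 1.22 to 1.45 unstructured and 1 + 0.3²/0.96 = 1.094 under compound symmetry.

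**CGQL, Weeks 6/10/18/26, correlations 0.6/0.5/0.4/0.3.** Week 26 is 1.035 to 1.059 unstructured, and 1 + (0.45 − 0.3)²/0.91 = 1.025 under compound symmetry. Week 10 is 1.000 to 1.003.

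**PDAI and EQ-5D, Weeks 6/10, correlations 0.55/0.4.** Week 10 is 1.009 to 1.011 unstructured, and 1 + 0.075²/0.84 = 1.007 under compound symmetry.

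**Cross-checks.**

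- With correlations decaying exponentially in time to between 0.8 and 0.2 at Week 10, visits at Weeks 3, 6 and 10 and equal SDs, the Week 10 ratio was at most 1.087 unstructured (about 4% in SE) and at most 1.041 under compound symmetry.
- With visits out to Week 26 in the same model, the Week 10 loss was 0.5% to 1.7% in SE unstructured and about 0% to 0.1% under compound symmetry.
- Simulation with 69 per arm and unstructured covariance gave a variance ratio of 1.08 for 0.7/0.55/0.4 at residual correlation 0.5 (formula 1.053). With about 8% dropout per visit depending on the last value it gave 1.075. Neither model showed material bias.

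**The case against.** The strongest reply is that nothing here is wrong. A single baseline covariate is a valid pre-specified model, randomisation keeps every visit contrast unbiased, and the loss depends on unequal slopes that the SAP gives no means of demonstrating. The larger figures also need equal SDs and an unstructured covariance, and neither is stated. All of this stands. It limits the point to a conditional efficiency gain that is very small for PDAI and EQ-5D and matters at most for stool frequency and late CGQL.

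It does not dispose of the point. The term costs almost nothing, and the SAP gives no reason for assuming equal slopes.

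Three stronger readings are tempting and are not supported:

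- **That the Week 10 contrast is definitely less precise.** With equal slopes the loss is exactly zero, and the SAP gives no correlation or SD to settle the matter.
- **That the last visits always suffer most.** Under compound symmetry the first visit can lose more, and the SAP names no covariance structure.
- **That the primary comparison at Week 10 is weakened.** The co-primaries are binary and tested by a stratified Cochran-Mantel-Haenszel test. Their power and the total of 138 do not depend on this model, and the Stool Frequency text does not single out Week 10 for it.

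**Conclusion.** The point holds as a conditional, minor efficiency improvement. As written, the model has one baseline slope for all visits and passes it on to the PDAI, CGQL and EQ-5D analyses. If the slopes differ, the visit-specific contrasts lose some precision without becoming biased.

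Under the assumed correlations the plausible cost is a few per cent of variance: up to about 8% for stool frequency at Week 10, up to about 6% for CGQL at Week 26, and about 1% for PDAI and EQ-5D. A much steeper fall in correlation would cost more. Rising SDs or compound symmetry would reduce the stool frequency figure to about 1% to 3%. All these sizes rest on assumed correlations, SDs and covariance.

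**What to change.** In section 1.3.2.2, Stool Frequency, add a baseline-by-visit interaction to the fixed effects. PDAI, CGQL and EQ-5D refer back to that model, so the term carries over without further edits.

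The cost is one extra degree of freedom for the two-visit models (PDAI, EQ-5D), two for stool frequency with three visits, and three for CGQL. It is a wording change only: no new data, visits or subjects. It should be made before unblinding. Section 1.4 already gives the blinded data review the tasks of considering further covariates and finalising the SAP.

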### **Urgency**

Urgency will be recorded for each bowel movement in the subject's diary as none (0), some urgency (1), great urgency (2), and subject soiled themselves, involuntarily (3). The frequency of each score in the 7 diary days prior to a study visit will be evaluated.

Changes from baseline in urgency score at week 6 will be summarized and compared between treatments.

The proportion of subjects recording urgency episodes with score 3 (fecal incontinence) after 3, 6 and 10 weeks of treatment will be analysed using logistic regression models including terms for region, treatment, sex, age group and baseline urgency.

### **Rectal Bleeding**

The frequency of rectal bleeding will be evaluated from the data recorded in the subject's diary for the 7 days prior to each study visit.

Changes from baseline in rectal bleeding at Week 6 will be summarized and compared between treatments.

